1.3.2 Cohort B

Table 2 Study Schedule of Activities – Cohort B

Study Period:	Screening	Intervention				EOT	Posttreatment			Notes
Visit Number/Title:	Screening	Cycle 1		Cycle 2 onwards*			Safety FU	Efficacy FU	Survival FU	*Cycles 2 to 17 for Q6W schedule; Cycle 2 to 35 for Q3W schedule.
Cycle Day	Up to 28 days prior to first dose	1	Day 22 (Q6W regimens only)	1	Day 22 (Q6W regimens only)	DC	30 days after last dose			
Scheduling Window (days):	-28 to -1	+3	±3	±3	±3		+7	Q9W ±7	Q12W ±14	
Administrative Procedures										
Informed Consent	X									If the investigator plans to treat beyond disease progression, the participant or their legally acceptable representative will be asked to provide documented informed consent (see Section 8.1.1.1).
Informed Consent for Future Biomedical Research (optional)	X									To be obtained after consenting to the main study.
Inclusion/Exclusion Criteria	X	X								
Participant Identification Card	X	X								Add the allocation number at the time of allocation.
Demographics and Medical History	X									
Oncologic Medical History (oncology disease status, MSI/MMR status and prior oncology treatment history including surgery)	X									
RAS (KRAS and NRAS) and BRAF mutation status	X									Results must be obtained by the site before C1D1 allocation. Only perform if status is not already known. Perform per institutional standards.

Study Period:	Screening	Intervention				EOT	Posttreatment			Notes
Visit Number/Title:	Screening	Cycle 1		Cycle 2 onwards*			Safety FU	Efficacy FU	Survival FU	*Cycles 2 to 17 for Q6W schedule; Cycle 2 to 35 for Q3W schedule.
Cycle Day	Up to 28 days prior to first dose	1	Day 22 (Q6W regimens only)	1	Day 22 (Q6W regimens only)	DC	30 days after last dose			
Scheduling Window (days):	-28 to -1	+3	±3	±3	±3		+7	Q9W ±7	Q12W ±14	
Prior/Concomitant Medication Review	X	X	X	X	X	X	X			Record concomitant medications beyond 30 days after treatment discontinuation if related to an SAE or ECI.
Randomization (via IRT)		X								To be completed after confirmation of eligibility.
Study Medication Administration		X		X*						*Required every 6 weeks for participants randomized to the MK-1308A or pembrolizumab monotherapy arms and every 3 weeks for participants randomized to the MK-4280A, MK-7684A, or MK-4830+pembrolizumab arms. Refer to Section 6.1.1.1 for study intervention information for participants in closed arms.
Progression and Subsequent Antineoplastic Therapy Status						X	X	X	X	All progression events and anticancer therapy will be recorded during follow-up until time of death or termination of survival follow-up. If a clinical visit is not feasible, follow-up information may be obtained by other means such as telephone or email. Not required for participants in closed arms.

Study Period:	Screening	Intervention				EOT	Posttreatment			Notes
Visit Number/Title:	Screening	Cycle 1		Cycle 2 onwards*			Safety FU	Efficacy FU	Survival FU	*Cycles 2 to 17 for Q6W schedule; Cycle 2 to 35 for Q3W schedule.
Cycle Day	Up to 28 days prior to first dose	1	Day 22 (Q6W regimens only)	1	Day 22 (Q6W regimens only)	DC	30 days after last dose			
Scheduling Window (days):	-28 to -1	+3	±3	±3	±3		+7	Q9W ±7	Q12W ±14	
Efficacy Assessments										
Tumor Scans (CT/MRI Chest, Abdomen, and Pelvis)	X							X		All imaging assessments should follow calendar days regardless of cycle delays. Tumor scans should be performed Q9W (±7 days), from the date of allocation or more frequently if clinically indicated. Refer to Section 8.2.1 for imaging information for participants in closed arms.
Survival Status	X								X	Survival follow-up begins after investigator determined disease progression or the start of new anticancer treatment. In addition, upon Sponsor request, participants may be contacted for survival status at any time during the study. Not required for participants in closed arms.

[figure not shown]
Study Period:	Screening	Intervention				EOT	Posttreatment			Notes
Visit Number/Title:	Screening	Cycle 1		Cycle 2 onwards*			Safety FU	Efficacy FU	Survival FU	*Cycles 2 to 17 for Q6W schedule; Cycle 2 to 35 for Q3W schedule.
Cycle Day	Up to 28 days prior to first dose	1	Day 22 (Q6W regimens only)	1	Day 22 (Q6W regimens only)	DC	30 days after last dose			
Scheduling Window (days):	-28 to -1	+3	±3	±3	±3		+7	Q9W ±7	Q12W ±14	
Patient-reported Outcomes										
CCI										

Study Period:	Screening	Intervention				EOT	Posttreatment			Notes
Visit Number/Title:	Screening	Cycle 1		Cycle 2 onwards*			Safety FU	Efficacy FU	Survival FU	*Cycles 2 to 17 for Q6W schedule; Cycle 2 to 35 for Q3W schedule.
Cycle Day	Up to 28 days prior to first dose	1	Day 22 (Q6W regimens only)	1	Day 22 (Q6W regimens only)	DC	30 days after last dose			
Scheduling Window (days):	-28 to -1	+3	±3	±3	±3		+7	Q9W ±7	Q12W ±14	
Vital Signs (temperature, HR, RR, DBP, SBP)	X	X	X	X	X	X	X			BP and pulse rate will be measured after the participant has been resting for 5 minutes. Include pulse oximetry (SpO2) if locally required.
12-lead ECG	X		X*	X*	X*	X				*As clinically indicated.
ECOG Performance Status	X	X	X	X	X	X	X			Must be performed within 3 days of C1D1 treatment and before treatment at each cycle.
AE/SAE review	X									AEs monitored up to 30 days after last dose. SAEs monitored up to 90 days and pregnancy monitored up to 120 days after last dose, or 30 days after last dose if participant starts a new anticancer therapy, whichever is sooner. Refer to Section 8.3 for safety monitoring information for participants in closed arms.
Laboratory Assessments										
Hematology/Chemistry	X	X*	X	X	X	X	X			Collect Predose. *Collect within 72 hours before first study intervention dose.
Urinalysis	X	X*	X*	X*	X*	X*	X			*As clinically indicated Collect within 72 hours before first study intervention dose.
Serum or Urine Pregnancy test (WOCBP only)	X	X		X		X	X			WOCBP require a negative test prior to allocation. If more than 24 hours for a urine test or 72 hours for a serum test have elapsed prior to the first dose of study intervention, another pregnancy test is required. See country-specific requirements in Appendix 7.

Study Period:	Screening	Intervention				EOT	Posttreatment			Notes
Visit Number/Title:	Screening	Cycle 1		Cycle 2 onwards*			Safety FU	Efficacy FU	Survival FU	*Cycles 2 to 17 for Q6W schedule; Cycle 2 to 35 for Q3W schedule.
Cycle Day	Up to 28 days prior to first dose	1	Day 22 (Q6W regimens only)	1	Day 22 (Q6W regimens only)	DC	30 days after last dose			
Scheduling Window (days):	-28 to -1	+3	±3	±3	±3		+7	Q9W ±7	Q12W ±14	
PT/INR and aPTT/PTT (baseline only)	X									Additional testing to be conducted as clinically indicated.
HIV, HBsAg, HCV	X*									*Only if required by local health authority. See country-specific requirements in Appendix 7.
Thyroid Function Tests (TSH, T3, T4), Cortisol, and ACTH**	X		X	X		X	X			Free T3 and Free T4 are acceptable if total T3 and total T4 are unavailable. After C1, retrospective review of thyroid function, ACTH and cortisol testing results is allowed when the results are not available prior to dosing. **ACTH testing is to be done as required per investigator's discretion.
Serum Tumor Marker (CEA)	X	X	X	X		X		X		Dosing permitted prior to results of CEA being known.

Study Period:	Screening	Intervention				EOT	Posttreatment			Notes
Visit Number/Title:	Screening	Cycle 1		Cycle 2 onwards*			Safety FU	Efficacy FU	Survival FU	*Cycles 2 to 17 for Q6W schedule; Cycle 2 to 35 for Q3W schedule.
Cycle Day	Up to 28 days prior to first dose	1	Day 22 (Q6W regimens only)	1	Day 22 (Q6W regimens only)	DC	30 days after last dose			
Scheduling Window (days):	-28 to -1	+3	±3	±3	±3		+7	Q9W ±7	Q12W ±14	

CCI

Study Period:	Screening	Intervention				EOT	Posttreatment			Notes
Visit Number/Title:	Screening	Cycle 1		Cycle 2 onwards*			Safety FU	Efficacy FU	Survival FU	*Cycles 2 to 17 for Q6W schedule; Cycle 2 to 35 for Q3W schedule.
Cycle Day	Up to 28 days prior to first dose	1	Day 22 (Q6W regimens only)	1	Day 22 (Q6W regimens only)	DC	30 days after last dose			
Scheduling Window (days):	-28 to -1	+3	±3	±3	±3		+7	Q9W ±7	Q12W ±14	
CCI										
Archival or Newly Obtained Tissue Collection	X									May use archival tissue sample obtained within 5 years of screening period.
CCI										

Study Period:	Screening	Intervention				EOT	Posttreatment			Notes
Visit Number/Title:	Screening	Cycle 1		Cycle 2 onwards*			Safety FU	Efficacy FU	Survival FU	*Cycles 2 to 17 for Q6W schedule; Cycle 2 to 35 for Q3W schedule.
Cycle Day	Up to 28 days prior to first dose	1	Day 22 (Q6W regimens only)	1	Day 22 (Q6W regimens only)	DC	30 days after last dose			
Scheduling Window (days):	-28 to -1	+3	±3	±3	±3		+7	Q9W ±7	Q12W ±14	

CCI

[figure not shown]
ACTH=adrenocorticotrophic hormone; ADA=antidrug antibodies; AE=adverse event; aPTT=activated partial thromboplastin time; BP=blood pressure; BRAF=B-Raf gene; C=cycle; CEA=carcinoembryonic antigen; CT=computed tomography; ctDNA=circulating tumor deoxyribonucleic acid; D=day; DBP=diastolic blood pressure; DC=discontinuation; ECG=electrocardiogram; ECI=event of clinical interest; ECOG=Eastern Cooperative Oncology Group; EORTC QLQ-C30=European Organisation for Research and Treatment of Cancer Quality of Life Questionnaire; EOT=end of treatment; ePRO=electronic patient-reported outcome; EQ-5D-5L=EuroQoL 5-dimension, 5-level scale; FU=follow-up; HBsAg=Hepatitis B surface antigen; HCV=Hepatitis C virus; HIV=human immunodeficiency virus; HR=heart rate; INR=international normalized ratio; IRT=interactive response technology; KRAS=Kirsten rat sarcoma viral oncogene homolog; MMR=mismatch repair; MRI=magnetic resonance imaging; MSI=microsatellite instability; NAb=neutralizing antibody; PK=pharmacokinetic; PRO=patient-reported outcome; PT=prothrombin time; PTT=partial thromboplastin time; Q6W=every 6 weeks; Q9W=every 9 weeks; Q12W=every 12 weeks; RAS=genes that makes the proteins called KRAS, HRAS, and NRAS; RNA=ribonucleic acid; RR=respiratory rate; SAE=serious adverse event; SBP=systolic blood pressure; SoA=schedule of activities; SpO2=oxygen saturation; T3=triiodothyronine; T4=thyroxine; TSH=thyroid-stimulating hormone; WOCP=women of childbearing potential.

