Sponsor may elect to close an arm, the enrollment or study procedures for other arms of the study will remain unaffected. In addition, there are no current plans to add more cohorts or to expand the existing cohorts in this study. At implementation of Amendment 05, the following treatment arms are considered closed: Cohort B: MK-4280A, Cohort B: MK-7684A, and Cohort B: MK-4830+pembrolizumab.

As of the Investigator Letter dated 16-DEC-2024, participants who were receiving MK-4280A were offered the option to continue study therapy until treatment completion or transition to pembrolizumab monotherapy, and participants who were receiving MK-7684A were discontinued from that study therapy and offered the option to transition to pembrolizumab monotherapy. As per the Investigator Letter dated 25-SEP-2023, the MK-4830+pembrolizumab arm was closed to enrollment; all ongoing participants were offered the option to continue study therapy until treatment completion or transition to pembrolizumab monotherapy.

Participants who opt to continue treatment with pembrolizumab monotherapy will remain on the same visit schedule as per the initial assignment.

Participants in closed arms with access to approved SOC (eg, immunotherapy, chemotherapy, targeted therapy) should be considered for discontinuation from the study. Participants in closed arms who are benefiting from pembrolizumab monotherapy, but unable to access it as SOC outside the study, may continue on study and receive treatment with pembrolizumab monotherapy until discontinuation criteria are met. The final required study visit will be the Safety Follow-up Visit.

Participants will be evaluated with tumor scans and RECIST 1.1 response assessment (chest, abdomen, and pelvis) Q9W (63 ± 7 days) from the date of allocation until disease progression is assessed by the site and verified by BICR or initiation of a new anticancer treatment. All scans obtained will be assessed by the BICR using RECIST 1.1 for determination of ORR and PFS. Refer to Section 8.2.1 for imaging information for participants in closed arms.

Survival follow-up will continue after disease progression is verified by BICR or the start of new anticancer treatment for participants in open arms. In addition, upon Sponsor request, participants may be contacted for survival status at any time during the study. Refer to Section 8.11.4 for posttreatment follow-up information for participants in closed arms.

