8.2 Efficacy/Immunogenicity Assessments

8.2.1 Tumor Imaging and Assessment of Disease

Throughout this section, the term ‘scan’ refers to any medical imaging data used to assess tumor burden and may include cross-sectional imaging (such as CT or MRI), medical photography, or other methods as specified in this protocol.

In addition to survival, efficacy will be assessed based on evaluation of scan changes in tumor burden over time, until the participant completes or is withdrawn from the study or goes into Survival Follow-up. The process for scan collection and transmission to the iCRO can be found in the SIM. Tumor scans by CT for the chest, abdomen, and pelvis, are strongly preferred. For the abdomen and pelvis, contrast-enhanced MRI may be used when CT with iodinated contrast is contraindicated, or when mandated by local practice. The same scan technique should be used in a participant throughout the study to optimize the reproducibility of the assessment of existing and new tumor burden and improve the accuracy of the response assessment based on scans.

Note: For the purposes of assessing tumor scans, the term “investigator” refers to the local investigator at the site and/or the radiological reviewer at the site or at an offsite facility.

If brain scans are performed, MRI is preferred; however, CT imaging will be acceptable, if MRI is medically contraindicated.

Bone scans may be performed to evaluate bone metastases. Any supplemental scans performed to support a positive or negative bone scan, such as plain X-rays acquired for correlation, should be submitted to the iCRO.

Other types of medical imaging (such as ultrasound) should not be submitted to the iCRO and will not be included in response assessment.

At Screening, participant eligibility will require radiographic documentation of at least one lesion that meets the requirements for selection as a target lesion, as defined by RECIST 1.1 assessed by the site and verified by BICR, prior to participant allocation.

All scheduled scans for all study participants will be submitted to the iCRO. In addition, a scan that is obtained at an unscheduled time point, for any reason (including suspicion of progression or other clinical reason), should also be submitted to the iCRO if it shows disease progression, or if it is used to support a response assessment. All scans acquired within the protocol-specified window of time around a scheduled scan visit are to be classified as pertaining to that visit.

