
When the investigator identifies radiographic progression per RECIST 1.1, BICR will perform expedited verification of radiologic disease progression and the results will be communicated to the study site and the Sponsor via email. In clinically stable participants, imaging will continue until disease progression has been verified by BICR as described in Section 8.2.1.2.

For participants in closed arms, imaging scans should no longer be submitted to the iCRO nor read by BICR. For participants in closed arms who are still on study treatment, deriving clinical benefit, and will continue study treatment until criteria for discontinuation are met, local tumor imaging should continue per local SOC schedule and local SOC method of assessment of imaging. In closed arms, all imaging as well as relevant objectives and endpoints will be assessed locally.

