8.2.1.2 Tumor Scans During the Study

The first on-study scan should be performed at 9 weeks (63 days \pm 7 days) from the date of allocation. Subsequent tumor scans should be performed every 9 weeks (63 days \pm 7 days) or more frequently if clinically indicated. Scan timing should follow calendar days and should not be adjusted for delays in cycle starts.

Scans are to be performed until disease progression is identified by the investigator and verified by the BICR, for participants in open arms, or until the start of new anticancer treatment, withdrawal of consent, or death, whichever occurs first.

Objective response should be confirmed by a repeat scan performed at least 4 weeks after the first indication of a response is observed. Participants will then return to the regular scan schedule, starting with the next scheduled time point. Participants who receive additional scans for confirmation do not need to undergo the next scheduled scan if it is fewer than 4 weeks later; scans may resume at the subsequent scheduled time point.

On-study brain or bone scans should be performed if clinically indicated or to confirm CR (if other lesions indicate CR and brain or bone lesions existed at baseline).

For participants who have surgery with curative intent during the study, scans must be performed at a minimum of no less than 4 weeks after surgery and no more than 8 weeks prior to the next treatment cycle. The last set of scans prior to restart of treatment will be used to establish a new baseline of tumor burden. Subsequent scans will be compared to this new baseline and the visit responses will be limited to PD, non-PD, or NE (not evaluable); these new post-operative images will be assessed every 9 weeks (63 days \pm 7 days) from the

new baseline scan date until disease progression is assessed by the site and verified by BICR or initiation of a new anticancer treatment.

While off study intervention, participants who undergo surgical resection of visible disease may demonstrate disease progression in non-surgical sites. In this instance, disease progression might not necessarily reflect resistance to study intervention. Accordingly, participants who develop isolated lesion/tumor growth post-operatively (eg, while off study intervention) may resume the previously assigned study intervention. The investigator must assess overall clinical benefit to the participant and consult the Sponsor prior to resuming study intervention.

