8.2.1.3 End-of-treatment and Follow-up Tumor Scans

If participants discontinue study intervention, tumor scans should be performed at the time of discontinuation (± 4 -week window) unless previous scans were obtained within 4 weeks of discontinuation. If participants discontinue study intervention due to documented disease progression, this is the final required tumor scan.

If participants discontinue study intervention without documented disease progression, every effort is to be made to monitor disease status by acquiring tumor scans using the same schedule calculated from the date of allocation (refer to Section 8.2.1.2).

Scans are to be continued until one of the following conditions are met:

- disease progression as defined by RECIST 1.1 verified by BICR
- the start of a new anticancer treatment
- pregnancy
- death
- withdrawal of consent
- the end of the study

Refer to Section 8.11.4 for posttreatment follow-up information for participants in closed arms.

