8.2.1.5 RECIST 1.1 Assessment of Disease

RECIST 1.1 will be used as the primary measure for assessment of tumor response, date of disease progression, and as a basis for all protocol guidelines related to disease status (eg, discontinuation of study intervention). Although RECIST 1.1 references a maximum of 5 target lesions in total and 2 per organ, this protocol allows a maximum of 10 target lesions in total and 5 per organ, if clinically relevant to enable a broader sampling of tumor burden.

Upon investigator-assessed disease progression, for participants in open arms, the indicative scans are to be submitted immediately to iCRO for BICR verification of progression. After submission of scan(s), the iCRO will email the assessment to the site and Sponsor.

If disease progression is not verified, the process continues as follows:

- If participant is clinically stable, continue study intervention per protocol
 - resume imaging per protocol schedule (\geq 4 weeks to next scan)
 - send scans to iCRO
 - continue local assessment
 - do not change investigator assessment of progression

- if subsequent scan(s) indicate progression, submit scan(s) to iCRO to request verification
- If the participant is not clinically stable, best medical practice is to be applied

Before stopping study intervention or imaging or starting new anticancer therapy in a participant who is clinically stable, communication with the Sponsor is required.

If disease progression is verified, the process continues as follows:

- investigator judgement will determine action
- if the participant is clinically stable and study intervention is to continue, communication with the Sponsor is required and a reconsent addendum must be signed
- obtain scans locally per original protocol schedule
- do not send scans to iCRO

[figure not shown]
Figure 2 illustrates the study intervention decision process involving verification of disease progression for participants.

- For the purpose of this decision process, lack of clinical stability is defined as:
 - unacceptable toxicity
 - clinical signs or symptoms indicating clinically significant disease progression
 - decline in performance status
 - rapid disease progression or threat to vital organs or critical anatomical sites (eg, CNS metastasis, respiratory failure due to tumor compression, spinal cord compression) requiring urgent alternative medical intervention

Refer to Section 8.2.1 for imaging information for participants in closed arms.

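### For open Cohort B arms, Table 2 starts survival follow-up at the investigator's progression call, in conflict with the rule to image until BICR verification; if sites act on it, BICR PFS and DOR can be informatively censored

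*Combined protocol and SAP*

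**What the plan says.** Two triggers are given for the same transition in open arms.

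- Section 1.3.2, Table 2, Survival Status row: "Survival follow-up begins after investigator determined disease progression or the start of new anticancer treatment".
- Section 4.1: "Survival follow-up will continue after disease progression is verified by BICR or the start of new anticancer treatment for participants in open arms".

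The transition matters because Section 8.2.1 has tumor burden assessed "until the participant completes or is withdrawn from the study or goes into Survival Follow-up".

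The imaging sections use the BICR trigger. Section 8.2.1.2: "Scans are to be performed until disease progression is identified by the investigator and verified by the BICR, for participants in open arms". Section 8.2.1: "In clinically stable participants, imaging will continue until disease progression has been verified by BICR". Section 8.2.1.5 deals with a site call that BICR does not verify: a clinically stable participant stays on the scan schedule and, "if subsequent scan(s) indicate progression, submit scan(s) to iCRO to request verification".

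Other places name progression without saying whose. Section 8.2.1.3: "If participants discontinue study intervention due to documented disease progression, this is the final required tumor scan", although the stop list in that section requires BICR verification. Section 8.11.3 sends participants who stop treatment for progression to Survival Follow-up after the safety visit. Section 8.11.4.2, and a parallel sentence in Section 4.1, give posttreatment imaging to those who stop for reasons other than progression.

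**The concern.** Central review is there to keep arm knowledge out of the response and progression data; Section 4.2.1.1 gives bias reduction as its purpose. The trial is open-label, so the investigator who calls progression knows the arm. If that call alone moves a participant into a phase without scans, the investigator also decides how long BICR can look for an event.

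A participant with a site call that BICR has not verified is probably at raised risk of BICR progression soon afterwards. Ending scans at that moment is informative censoring. If it happens equally often in both arms, PFS and DOR look too long. If it happens more often in one arm, the PFS hazard ratio is distorted as well. Scans that were not taken cannot be recovered at analysis.

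**Working it through.** **1. Which text governs?** Table 2 and Section 4.1 name the same pair of triggers, progression or new anticancer treatment, but differ on who establishes progression. Following Table 2 literally together with the Section 8.2.1 sentence on Survival Follow-up, scans end at the site's call. Following 8.2.1.2, 8.2.1.5 and the stop list in 8.2.1.3, they continue until BICR verifies. The opening of Section 8 calls adherence to the Schedule of Activities essential and required, so a site could reasonably treat the table note as binding.

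**2. What happens in the analysis?** Section 9.6.1.3 counts BICR-documented progression or death as PFS events. With neither event and no new therapy, Table 10 censors at the last disease assessment. A death immediately after two or more missed assessments is censored too; at 9-week intervals that means roughly beyond 2 × 9 = 18 weeks after the last scan. Table 9 treats DOR similarly, and Section 9.1 lists BICR DOR as the key secondary endpoint.

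**3. How large could it be?** The plan has no figure to reproduce: no rate of disagreement between site and BICR is given, and the cohort sizes and power text are redacted. What follows is a hypothetical range.

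Input from the documents: median PFS on pembrolizumab of 16.5 months (Section 2.1, first-line phase 3 trial). Assumptions: exponential PFS with the same hazard λ = ln 2/16.5 in both arms; in a fraction p of an arm, scans stop at a site call that precedes BICR progression by an exponential lag with median 3 months; no later event is counted for these participants.

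At time t, events occur at rate λ(1 − p)e^(−λt). The proportion still at risk is e^(−λt)[(1 − p) + p·k], where k = (1/3)/(1/3 + 1/16.5) = 16.5/19.5 = 0.846. The observed hazard is therefore λ·g(p), with g(p) = (1 − p)/[(1 − p) + 0.846p].

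- g(0.10) = 0.90/0.9846 = 0.914
- g(0.20) = 0.80/0.9692 = 0.825
- g(0.25) = 0.75/0.9615 = 0.780

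Hazard ratio, experimental to control = g(p experimental)/g(p control); the true value is 1.00.

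| Scans stopped, control | Scans stopped, experimental | Hazard ratio |
|---|---|---|
| 20% | 10% | 0.914/0.825 = 1.11 |
| 25% | 10% | 0.914/0.780 = 1.17 |
| 10% | 20% | 0.825/0.914 = 0.90 |
| 20% | 20% | 1.00 |

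In the last row the observed median is 16.5/0.825 = 20.0 months instead of 16.5. A simulation of this model with 300,000 participants per arm gives the same values.

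**4. Does it depend on the model?** A second simulation used 9-week scans, a 36-month cutoff, a true hazard ratio of 0.70 and a site call one scan before BICR progression (20,000 per arm). With 20% of control and 10% of experimental participants affected, the hazard ratio moves from about 0.70 to 0.77. With 20% in both arms it stays near 0.70, while the control median moves from 16.6 to 20.7 months. Direction and rough size agree.

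**The case against.** The strongest reply is that Section 8.2.1.5 addresses this very case. For a clinically stable participant whose progression BICR does not verify, imaging resumes on schedule, scans go to the iCRO, and the Sponsor must be contacted before imaging stops. Sections 8.2.1, 8.2.1.2 and the stop list in 8.2.1.3 point the same way, and Section 4.1 refers the reader to Section 8 for procedural detail. The Table 2 note sits in the Survival Status row; the Tumor Scans row above it carries no stop at the investigator's call. All of this stands, and it makes the risk conditional.

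It does not remove the conflict. The safeguard is limited to clinically stable participants, and the documents do not say that Section 8 overrides a schedule they call required. It can also be said that Section 4.1 speaks of survival follow-up continuing rather than beginning. Even on that reading, the Table 2 trigger combined with Section 8.2.1 still conflicts with 8.2.1.2.

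Three stronger readings are tempting and not supported:

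- A reader might infer that informative censoring is built into the plan. It needs a site to follow the table note, BICR not to have verified progression, no new therapy, and no death soon enough to count. Participants who start new therapy before a BICR event are censored under Table 10 either way.
- A reader might take documented progression in 8.2.1.3, or plain progression in 8.11.3, to mean the investigator's call. The text does not say so; it is unspecific rather than contradictory.
- A reader might take the hazard ratios above as estimates for this trial. The documents contain no evidence that disagreement with BICR differs by arm.

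**Conclusion.** The inconsistency is real and in current text, and it should be corrected. It concerns the open Cohort B arms, MK-1308A and pembrolizumab monotherapy at Amendment 05. Closed arms have neither BICR reads nor survival follow-up, and the matching Cohort A rows are not visible in the available text. The endpoints exposed are BICR PFS, which is secondary and analyzed by estimation, and BICR DOR; the primary ORR is little affected.

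If sites act on the table note, the hypothetical range is a null hazard ratio moved to between 0.90 and 1.17 for imbalances of 10 to 15 percentage points, and a median overstated by about 3.5 months (20.0 − 16.5) when 20% of both arms are affected. Those sizes rest wholly on assumed stopping rates and an assumed lag. The conflict between the sections does not depend on them.

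**What to change.** For open arms, and for imaging and data collection only:

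1. In Table 2, Survival Status row, replace the investigator-determined trigger with BICR-verified progression, matching Sections 4.1 and 8.2.1.2.
2. In 8.2.1.3 (the final-scan sentence) and 8.11.3, state that progression means BICR-verified progression.
3. Amend 8.11.4.2 and the parallel sentence in Section 4.1 so that a participant who stops study intervention for progression not verified by BICR enters Efficacy Follow-up, with 9-weekly scans sent to the iCRO until BICR-verified progression, new anticancer therapy or another listed stop condition. Without this step, such a participant would fit neither follow-up path once 8.11.3 is changed.
4. Check the corresponding Cohort A rows for the same wording.

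The cost is protocol wording. No scans are added beyond those 8.2.1.2 already requires, and the rules for continuing or stopping treatment are untouched. The change is useful only while open-arm imaging follow-up continues.
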